## 10. ADVERSE EVENT REPORTING

## 10.1 Definitions

An **Adverse Event** (AE) is “any untoward medical occurrence in a patient or clinical trial subject administered a medicinal product and which does not necessarily have a causal relationship with this treatment”.

An AE can therefore be any unfavourable and unintended sign (including abnormal laboratory finding), symptom, or disease temporally associated with the use of a medicinal product, whether or not considered related to the medicinal product.

An **Adverse Drug Reaction (ADR)** is an “untoward and unintended response to an investigational medicinal product related to any dose administered”.

Within this trial the causality of an AE has to be considered with regards to the placebo and its excipients.

All AEs judged by either the reporting Investigator or the Sponsor as having a reasonable causal relationship to a medicinal product qualify as adverse reactions. The expression “reasonable causal relationship” means to convey in general that there are facts (evidence) or arguments meant to suggest a causal relationship.

The definition covers also medication errors and uses outside what is foreseen in the protocol, including misuse and abuse of the product.

**A Serious Adverse Event (SAE)/Serious ADR** is any untoward medical occurrence or effect that, at any dose, falls in one or more of the following categories:

## • Results in death

Death is not an AE but an outcome. It is the cause of death that should be regarded as the AE. The only exception to this rule is “sudden death” where no cause has been

|  |                      |
|--|----------------------|
| Clinical Study Code No.: CLI-05993AB6-07 | Version No.: 2.0     |
| EUDRACT No.: 2022-000536-36              | Date: 30 August 2022 |

established; in this latter instance, “sudden death” should be regarded as the AE and “fatal” as its reason for being serious;

- **Is life-threatening**

Life-threatening refers to an event in which the patient was at risk of death at the time of the event (e.g. aplastic anaemia, acute renal failure, and anaphylaxis). The term does not refer to an event which hypothetically might have caused death if it were more severe;

- **Requires hospitalisation or prolongation of existing hospitalisation**

Hospitalisation refers to a situation whereby an AE is associated with unplanned formal overnight admission into hospital, usually for purpose of investigating and/or treating the AE. Hospitalisation for the treatment of a medical condition that occurs on an “elective” or “scheduled” basis or for a pre-existing condition that did not worsen during the study should not necessarily be regarded as an AE. Complications that occur during the hospitalisation are AEs. If a complication prolongs hospitalisation, the event is an SAE. Emergency room visits that do not result in a formal admission into hospital should be evaluated for one of the other seriousness criteria (e.g. life-threatening; persistent or significant disability or incapacity; medically significant);

- **Results in persistent or significant disability or incapacity**

The term significant disability should be viewed as any situation whereby an AE has a clinically important effect on the subject’s physical or psychological well-being to the extent that the subject is unable to function normally;

- **Is a congenital anomaly or birth defect;**

- **Is a medically significant AE**

This criterion allows for any situations in which important AEs/reactions that are not immediately life-threatening or do not result in death or hospitalisation may jeopardise the subject’s health or may require intervention to prevent one of the above outcomes. Examples of such events are: intensive treatment in an emergency room or at home for allergic bronchospasm; blood dyscrasias or convulsions that do not result in hospitalisation; or development of drug dependency or drug abuse.

Medical and scientific judgment should be exercised in deciding whether an event is serious because medically significant.

Any suspected transmission via a medicinal product of an infectious agent is also considered a serious ADR.

A **Non-Serious Adverse Event/Non-Serious ADR** is an AE or ADR that does not meet the criteria listed above for an SAE/serious ADR.

## **10.2 Expectedness**

Since no active ingredient will be included in the study treatment but only pMDI containing placebo propellant and excipients will be administered, there is no reference document for the assessment of the expectedness of AEs in this study. All AEs assessed as related to the study treatments and/or their excipients will be considered as unexpected AEs for safety reporting purposes.

|  |                      |
|--|----------------------|
| Clinical Study Code No.: CLI-05993AB6-07 | Version No.: 2.0     |
| EUDRACT No.: 2022-000536-36              | Date: 30 August 2022 |

### **10.3 Intensity of Adverse Event**

Each AE must be rated on a 3-point scale of increasing intensity:

- **Mild:** the event causes a minor discomfort or does not interfere with the daily activities of the subject or does not lead to either modification of test treatment dosage or establishment of a correcting treatment;
- **Moderate:** the event perturbs the usual activity of the subject and is of a sufficient severity to make the patient uncomfortable. The event leads to a diminution of dosage of the test treatment, or a temporary interruption of its administration or to the establishment of a correcting treatment;
- **Severe:** the event prevents any usual routine activity of the subject and causes severe discomfort. It may be of such severity to cause the definitive interruption of test treatment.

### **10.4 Causality Assessment**

The following “binary” decision choice will be used by the Investigator to describe the causality assessment:

- Reasonable possibility of relatedness;
- No reasonable possibility of relatedness.

The expression “reasonable possibility of relatedness” is meant to convey, in general, that there are facts (evidence) or arguments meant to suggest a causal relationship.

The Investigator will be asked to consider the following before reaching a decision on causality assessment:

- Time relationship between study treatment intake and event’s onset;
- Dechallenge (did the event abate after stopping the study treatment?);
- Rechallenge (did the event reappear after reintroduction of the study treatment?);
- Medical history;
- Study treatment(s);
- Mechanism of action of the study treatment;
- Class effects;
- Other treatments - concomitant or previous;
- Withdrawal of study treatment(s);
- Lack of efficacy/worsening of existing condition;
- Erroneous treatment with study medication (or concomitant);
- Protocol-related process.

### **10.5 Action Taken with the Study Treatment Due to an Adverse Event**

- Dose not changed;
- Treatment permanently withdrawn;
- Unknown;
- Not applicable.

|  |                      |
|--|----------------------|
| Clinical Study Code No.: CLI-05993AB6-07 | Version No.: 2.0     |
| EUDRACT No.: 2022-000536-36              | Date: 30 August 2022 |

## **10.6 Other Actions Taken**

- Specific therapy/medication;
- Concomitant procedure.

## **10.7 Outcome**

Each AE must be rated by choosing among:

- Recovered/resolved;
- Recovering/resolving;
- Not recovered/not resolved;
- Recovered with sequelae/resolved with sequelae;
- Fatal;
- Unknown.

## **10.8 Recording Adverse Events**

All AEs occurring during the course of the study must be documented in the AE page of the eCRF. Moreover, if the AE is serious, the SAE Form must also be completed.

It is the responsibility of the Investigator to collect all AEs (both serious and non-serious) derived by spontaneous, unsolicited reports of subjects, by observation and by routine open questionings.

The recording period for AEs is the period starting from the signature of the ICF until the subject's study participation ends.

Any CS abnormalities detected at screening (Visit 1) not due to a pre-existing condition or CS changes at the following visits in the medical opinion of the Investigator must be reported as AEs in the eCRF.

If a CS abnormal laboratory finding or other abnormal assessment meets the definition of an AE, then the AE page of the eCRF must be completed, as appropriate. A diagnosis, if known, or clinical signs and symptoms if diagnosis is unknown, rather than the CS abnormal laboratory finding, should be reported on the AE page of the eCRF. If no diagnosis is known and clinical signs and symptoms are not present, then the abnormal finding should be recorded.

For pharmacovigilance purposes, all SAEs should be followed-up in order to elucidate as completely and practically as possible their nature and/or causality until resolution of all queries, clinical recovery is complete, laboratory results have returned to normal, stable condition is reached or until the subject is lost to follow-up. Follow-up may therefore continue after the subject has left the study. In this case, the follow-up will continue with no timelines for related SAEs, while for unrelated SAEs the type and extent of follow-up undertaken will be determined for each individual case and will depend upon the nature (e.g. events with poor prognosis or which do not resolve), severity and medical significance of the event.

## **10.9 Reporting Serious Adverse Events to Chiesi**

The Investigator must report all SAEs to the █ Safety Contact listed below within 24 h of awareness. The information must be sent by providing the completed Serious Adverse Event

|  |                      |
|--|----------------------|
| Clinical Study Code No.: CLI-05993AB6-07 | Version No.: 2.0     |
| EUDRACT No.: 2022-000536-36              | Date: 30 August 2022 |

paper form. At a later date, the █ Safety Contact will report all information to Chiesi Global Pharmacovigilance, the Clinical Project Manager and the Clinical Research Physician.

| Safety Contact        | Fax no.    | E-mail     |
|-----------------------|------------|------------|
| █ Safety Contact      | ██████████ | ██████████ |
| Chiesi Safety Contact | ██████████ | ██████████ |

Reporting of SAEs from the investigational site is from the time of a subject's signature of the ICF and until the subject's study participation ends. After this date, even if no active monitoring of subjects is required, SAEs occurring to a subject should be reported if the Investigator becomes aware of them.

Up to the closure of the investigational site, SAE reports should be reported to the █ Safety Contact. New SAEs occurring after the site is closed should be reported directly to the Chiesi Safety Contact.

#### **10.10 Reporting Serious Adverse Events to Regulatory Authorities/Ethics Committees**

All SUSARs, which occur with the investigational medicinal products within or outside the concerned clinical trial, if required, will be reported in compliance with the timelines and standards for reporting SUSARs according to local UK regulations. The Medicines and Healthcare products Regulatory Agency (MHRA) will be informed through MHRA Individual Case Study Report (ICSR) Submission portal, while the EC and the Investigators by Council for International Organizations of Medical Sciences (CIOMS) I form or by periodic line-listings produced by Chiesi Global Pharmacovigilance.

With regard to regulations in force for Pharmacovigilance, the Investigator must fulfil his/her obligation according to the law in force in the UK.

#### **10.11 General Notes**

- In case of death, a comprehensive narrative report of the case should be prepared by the Investigator and sent to the █/Chiesi Safety Contact together with the SAE form, retaining a copy on site.
- If an autopsy is performed, copy of autopsy report should be actively sought by the Investigator and sent to the █/Chiesi Safety Contact as soon as available, retaining a copy on site.
- All documents provided by the Investigator or site staff to the █ Safety Contact must be carefully checked for respect of confidentiality. All personal subject's data must be redacted.
- In case of pregnancy, the subject will be immediately withdrawn from the study and she will be asked (with a separate consent) to be followed with due diligence until the outcome of the pregnancy is known and till the age of one year of the child, to detect any congenital anomaly or birth defect. The pregnancy must be reported by the Investigator within 24 h by fax/e-mail to the █/Chiesi Safety Contact using the paper

|  |                      |
|--|----------------------|
| Clinical Study Code No.: CLI-05993AB6-07 | Version No.: 2.0     |
| EUDRACT No.: 2022-000536-36              | Date: 30 August 2022 |

Pregnancy Report Form. The [REDACTED] Safety Contact will inform Chiesi of the pregnancy within one working day of being notified.

The first two pages of the Pregnancy Report Form should be completed by the Investigator with all the available information and sent to the [REDACTED]/Chiesi Safety Contact. Information collected in specific sections relative to the pregnancy will be recorded in the form only upon signature of the specific ICF by the subject/subject's partner. The third page will be completed as soon as the Investigator has knowledge of the pregnancy outcome, together with a follow-up of the first two pages, if necessary (e.g. an update in the medications received during pregnancy by the mother). If it meets the criteria for immediate classification of a SAE (e.g. spontaneous or therapeutic abortion, stillbirth, neonatal death, congenital anomaly, birth defect) the Investigator should follow the procedure for reporting SAEs.

If it is the partner, rather than the subject, who is found to be pregnant, the same procedure regarding pregnancy reporting is to be followed and the Pregnancy Report Form should be completed, but the subject participating to the study should not be discontinued from the study.

- If the pregnancy is discovered before taking any dose of study treatment, the pregnancy does not need to be reported; it is only required that the subject is immediately withdrawn from the study.
- Any ADR occurring with any marketed non-investigational medicinal product and/or concomitant medication during the study must be reported by the Investigator to his/her concerned Health Authority according to the applicable laws. The Investigator is also recommended to report all ADRs to the relevant Marketing Authorisation Holders of the involved medicinal products. Additionally, conditions of use outside the marketing authorisation of the medicinal products (i.e. off-label, overdose, misuse, abuse and medication errors) or from occupational exposure, as well as cases of suspected drug interaction, pregnancy, breast-feeding exposure and lack of efficacy should be reported.

## 11. DATA MANAGEMENT

An eCRF will be filled-in by the Investigator and/or his/her representative designee.

Front-end edit checks will run at the time of data collection and back-end edit checks will be used by the Data Manager to check for discrepancies and to ensure consistency and completeness of the data.

Questionnaires will be collected on paper and data will be entered in the database by trained and authorised site personnel.

Medical history, AEs and concomitant procedures will be coded using the Medical Dictionary for Regulatory Activities (MedDRA); medications will be coded using the World Health Organization (WHO) Drug dictionary and Anatomical Therapeutic Chemical (ATC) classification.

External data for spirometry assessments will be processed centrally, sent to the designated CRO and reconciled with the corresponding information recorded in the eCRF.

Access to electronic systems used for data collection will be granted to the study personnel only after appropriate training.

|  |                      |
|--|----------------------|
| Clinical Study Code No.: CLI-05993AB6-07 | Version No.: 2.0     |
| EUDRACT No.: 2022-000536-36              | Date: 30 August 2022 |

After the completion of data collection and cleaning, a review meeting will be held to determine the occurrence of any protocol violation and to define the subject populations for the analysis. Once the database has been declared to be complete and accurate, it will be locked, the randomisation codes will be opened, and the planned statistical analyses will be performed.

If the database is unlocked after the initial lock, the process must be carefully controlled and documented; updates to the study data must be authorised by Chiesi.

At the study conclusion, a complete copy of the study data will be created for archival purposes at Chiesi. The Investigators will receive copies of the subject data for retention at the investigational sites.

## 12. STATISTICAL METHODS

### 12.1 Sample Size

The sample size has been calculated to verify equivalence between the test treatment (HFA-152a) and the reference treatment (HFA-134a) for the relative change from baseline in FEV1 at the 15 min post-dose timepoint, with equivalence defined as a difference between the two treatments within the 10% (i.e. [-10%; +10%]).

A total of 20 evaluable subjects will ensure a 95% power to provide a 95% confidence interval (CI) of the mean difference of the relative change from baseline in FEV1 at 15 min post-dose within the above-mentioned equivalence limits (i.e. [-10%; +10%]) assuming a within-subject standard deviation (SD) of 8%.

Estimating a non-evaluable rate of 16%, a total of 24 subjects will be randomised.

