## **1.2 Study Rationale**

This clinical study has been designed to investigate the potential for bronchoconstriction of the new HFA-152a propellant, in comparison with the marketed HFA-134a propellant.

This study was conceived following concerns from the European Medicines Agency's (EMA) Committee for Medicinal Products for Human Use (CHMP) about the lack of data on the potential of the new HFA-152a propellant to cause bronchoconstriction in healthy subjects or asthma patients with hyperreactive airways. In fact, safety studies performed during the clinical development programme assessed the safety of the HFA-152a propellant when used for the administration of asthma treatments via pMDI. According to the CHMP, these studies were not capable of assessing the potential for bronchoconstriction of the new propellant, which may be clinically relevant but not detected, given that the HFA-152a propellant was administered in combination with bronchodilating agents.

As this residual risk was deemed not adequately covered by the clinical development program, and as it cannot be predicted by *in-vitro* data, this appropriately designed clinical trial will adequately address this residual risk.

This randomised, double-blind, controlled, 2-way cross-over study will be conducted in male and female subjects with mild asthma (Step 1 of the Global Initiative for Asthma [GINA] 2021 guidelines). Each subject will be administered a single-dose [REDACTED] of each of the two following treatments, according to an order pre-specified by the randomisation list:

- **Test treatment:** placebo HFA-152a propellant via pMDI;
- **Reference treatment:** placebo HFA-134a propellant via pMDI.

|  |                      |
|--|----------------------|
| Clinical Study Code No.: CLI-05993AB6-07 | Version No.: 2.0     |
| EUDRACT No.: 2022-000536-36              | Date: 30 August 2022 |

Subjects will be asked to wash-out from their asthma treatments before the administration of the study treatment and before the spirometry assessments, in order to suppress the bronchodilating effect of the asthma treatments. The following wash-out periods will apply:

- Inhaled/nebulised short-acting  $\beta$ 2-agonists (SABA): 6 h;
- Inhaled corticosteroids (ICS) (in combination with SABA): 24 h;
- ICS-formoterol: 24 h.

The selected treatment dose (██████████) corresponds to the maximum total daily dose of propellant allowed for administration with the Clenil pMDI device.

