- If the date(time) is missing or incomplete for a specific post-dose time point, then it will be imputed as the date(time) of the previous time point + the theoretical time interval between the two time points.
- If 2 or more consecutive post-dose time points have a missing or incomplete date(time), then the AUC will also be set to missing.

For FEV₁, the following abnormality categories are defined:

- Relative changes from baseline:
 - Decrease from Baseline >15 %

Potential exclusion of lung function parameters based on time window not respected will be discussed during the review of the data by the Chiesi team. Decisions on whether values are to be excluded from the analysis will be fully documented in the DRR.

2.5.3 *Inferential statistics*

Primary objective (i.e. evaluation of the potential for bronchoconstriction of each propellant):

- The relative change from baseline in FEV₁ at the 15 min post-dose time point will be analysed using an analysis of covariance (ANCOVA) model, including treatment group, subject and period as fixed effects, and FEV₁ baseline (mean of the two measurements at 45 min and 15 min pre-dose in each treatment period) as a covariate.

The adjusted mean relative change from baseline obtained with each treatment and the adjusted mean difference between HFA-152a and HFA-134a with their 95% CIs and p-values will be estimated by the model.

	Statistical Analysis Plan	
CLI-05993AB6-07		Final 1.0 of 22DEC2022

Other variables completing the evaluation of the potential for bronchoconstriction of each propellant:

- The relative changes from baseline in FEV₁ at all the other post-dose time points (5 min, 30 min, 1 h, 1 h 30 min and 3 h) will be analysed using the same model used for the relative change from baseline in FEV₁ at 15 min post-dose;
- The absolute changes from baseline in FEV₁ at all post-dose time points (5 min, 15 min, 30 min, 1 h, 1 h 30 min and 3 h) will be analysed using the same model used for the relative change from baseline in FEV₁ at 15 min post-dose.

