2.5.4 Presentation of results

Lung function parameters will be summarised by means of descriptive statistics at each analysis time point by treatment. Actual values, absolute and relative changes from baseline (FEV₁ and PEF only) will be tabulated.

For the ANCOVA models, adjusted mean in each treatment and the adjusted mean difference between HFA-152a and HFA-134a, their 95% CIs and related p-values will be provided and tabulated from the ANCOVA. This tables will also include the type III p-values associated to model effects.

The number and percentage of subjects with FEV₁ abnormal relative changes from baseline will be presented at each post-dose time point and at the worst-case analysis visit by treatment.

The change from baseline in FEV₁ AUC_{0-3h} will be summarised by means of descriptive statistics by treatment.

All lung function parameters will be listed.

Graphs of the mean changes (both absolute and relative) from baseline over time will be prepared for FEV₁ and PEF by treatment.

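### Equivalence is judged only on the mean FEV1 change at 15 min, and individual falls above 15% are counted per propellant without a within-subject comparison or interval

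*Protocol*

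**What the plan says.** Equivalence is defined in the sample-size text (Protocol 12.1, repeated in the protocol outline and SAP 1.3) on the difference in mean relative FEV1 change at 15 min, "with equivalence defined as a difference between the two treatments within the 10% (i.e. [-10%; +10"%]). The size follows from it: "A total of 20 evaluable subjects will ensure a 95% power to provide a 95% confidence interval (CI) of the mean difference" inside those limits, "assuming a within-subject standard deviation (SD) of 8"%. The readable text gives no reason for choosing 10 points.

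The analysis sections (Protocol 12.3.6, SAP 2.5.3) specify an ANCOVA with the adjusted mean difference, its 95% CI and a p-value. They do not restate the margin or give a decision rule.

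For individual subjects, SAP 2.5.2 defines one abnormality category for FEV1: "Decrease from Baseline >15"%. SAP 2.5.4 says that FEV1 "abnormal relative changes from baseline will be presented at each post-dose time point and at the worst-case analysis visit by treatment". Table 14.3.7.6 does this on the Safety set only. No cross-tabulation of the two periods within subject, no paired difference and no interval is planned for these falls.

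Protocol 1.2 explains that the trial answers a regulator's concern about bronchoconstriction, including in patients with hyperreactive airways, "which may be clinically relevant but not detected" in earlier studies because the propellant was given together with bronchodilators.

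**The concern.** The regulator's question is partly about susceptible subjects. If only some subjects react, the mean difference moves by the reactor share times the size of the fall, so a marked reaction in a minority can sit well inside ±10 points. The output closest to that question is the count of falls above 15%, and it appears as two separate columns.

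In a cross-over each subject is their own control. The informative quantity is how many fall on HFA-152a only, compared with how many fall on HFA-134a only. Two marginal counts do not show this, and without an interval they do not say how large an excess the trial can rule out. The report could then state equivalence of means and leave the reader unable to bound excess individual reactions.

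**Working it through.** **Inputs from the documents.** Margin ±10 points; two-sided 95% CI; within-subject SD 8%; 20 evaluable subjects; "Estimating a non-evaluable rate of 16%, a total of 24 subjects will be randomised"; 2x2 cross-over (Protocol 6.5 and 12.1).

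**Assumptions not in the documents.** True difference 0 for the plan's own calculation, since none is stated. For the illustration: 25% of subjects have an extra 15-point fall on HFA-152a and the rest have none. For the counts: changes on HFA-134a are normal with mean 0 and SD 8.

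**1. The plan's own figure.**
- n = 2 × 8² × (1.96 + 1.96)² / 10² = 19.67, rounded up to 20.
- At n = 20, SE = 8 × √(2/20) = 2.53. Normal-approximation power = 2Φ(10/2.53 − 1.96) − 1 = 95.4%. The stated 95% reproduces.
- With the t distribution on 18 df, power is 92.4%.
- 20/0.84 = 23.8, so 24 randomised also reproduces.

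**2. Reactor illustration at n = 20.**
- Mean difference = 0.25 × (−15) = −3.75 points.
- SD of the paired difference = √(2 × 8² + 15² × 0.25 × 0.75) = 13.05.
- SE = 13.05/√20 = 2.92. CI half-width = 2.101 × 2.92 = 6.13.
- A typical lower limit is −3.75 − 6.13 = −9.88, just inside −10.
- Simulation (100,000 cross-over trials, t interval on n−2 df): the criterion is met in 52% of trials with 20 subjects and 61% with 24.

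**3. Sensitivity at n = 20, one input varied at a time.**

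| Varied input | Criterion met |
|---|---|
| Within-subject SD 6 | 69% |
| Within-subject SD 10 | 36% |
| Reactor share 10% | 81% |
| Reactor share 20% | 63% |
| Reactor share 30% | 42% |

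If the planned 8% is taken to include the reactor heterogeneity already, the figures are 64% (n=20) and 73% (n=24).

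**4. Falls above 15% expected at 15 min in the same illustration.**
- HFA-134a: Φ(−15/8) = 3.0%, or 0.6 of 20.
- HFA-152a: reactors are centred on −15, so half of them cross the line: 0.25 × 0.50 + 0.75 × 0.030 = 14.8%, or 3.0 of 20.
- Among simulated trials that meet ±10, the HFA-152a count averages about 2.2 of 20.

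**5. What a paired table could bound.** If 0 of 20 subjects fall on HFA-152a only, the exact upper 95% limit for that share is 1 − 0.025^(1/20) = 16.8%. If 3 of 20 do, the exact interval is 3.2% to 37.9%.

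**6. Would a paired test help?** Exact McNemar at 15 min under the illustration has about 4% power with 20 subjects and 7–8% with 24. Among trials that meet ±10, it is significant in roughly 0.3% (n=20) and 1.4% (n=24).

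**The case against.** The case on the other side is substantial, and much of it stands.

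- **An average-equivalence test is meant to pass a true difference inside its margin.** A mean difference of −3.75 lies inside ±10, and a uniform −10 shift passes only 2.5% of the time, as designed. This stands: the criterion is not miscalculated. The limit is in what a mean can show.
- **The scenario is invented.** No passage supports a 25% reactor share or a 15-point fall. This stands, so the pass rates are an illustration with a range and not a property of HFA-152a.
- **Other outputs bear on individual reactors.** The plan has bronchospasm and cough among the adverse events of particular interest, rescue use within 3 h, minimum and maximum relative FEV1 change at each time point, and Listing 16.2.8.4, which flags abnormal changes by subject. This stands, so the count is not the only such output. None of these gives an interval for the excess of reactors.
- **The unpaired counts already carry a signal.** In the illustration they are higher on HFA-152a in about 77% (n=20) or 84% (n=24) of the trials that meet ±10. This also stands, but a higher count without an interval does not say what excess remains possible.

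A reader might infer that a quarter of subjects could have a reaction that the SAP calls abnormal while the trial reads as equivalent. The documents do not support that. The SAP category is a fall of more than 15% from baseline, not 15 points more than on the reference; under the assumed model about 3 of 20 cross it at 15 min, not 5.

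A reader might also infer that the count plays no part in the conclusion. Protocol section 9 lists it among the variables that complete the evaluation of bronchoconstriction, and no decision rule is stated either way.

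**Conclusion.** The point holds as a worthwhile, inexpensive improvement. Equivalence is defined only on a mean at one time point, and falls above 15% are reported only as separate counts per propellant. Under the assumed 25% share and 15-point extra fall, with SD 8, the ±10 criterion is met in about 52% of trials with 20 subjects and 61% with 24. At n=20 this is roughly 36% to 81% over SDs of 6 to 10 and reactor shares of 10% to 30%, each varied alone. The expected falls above 15% at 15 min are then about 3.0 against 0.6 of 20. Rates at any time point were not modelled.

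A reader might infer that the margin itself is wrong because no reason is given for it. The documents do not show that. The absent rationale is a missing detail, and the ±10 points and the sample size can stay.

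**What to change.** Keep the sample size and the ±10 limits.

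1. In SAP 2.5.4 and Table 14.3.7.6, add a within-subject 2x2 table of FEV1 falls above 15%: HFA-152a only, HFA-134a only, both, neither. Give the paired difference in proportions with its 95% CI (for example Tango's score interval).
2. Do this at 15 min and at any post-dose time point. For the latter, use the worst-case definition in SAP 5.2.5, including unscheduled assessments, so that the table agrees with the existing any-time row.
3. Produce it on the Safety and PP sets. Present it as an estimate and omit a McNemar test: its power is so low that a non-significant p-value would reassure falsely.
4. Word the ANCOVA conclusion as equivalence of mean change at 15 min, and report it together with the paired interval.

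The cost is SAP text and one extended table (a PP version included), from data already collected, with no new subjects or procedures. The downside is a wide interval with 20 to 24 subjects, as step 5 of the working shows, and a narrower equivalence claim.
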